The aim of this study is to compare two modes of epidural analgesia delivery, PIEB versus CEI with PCEA dosing, in the treatment of labor pain. Our primary outcome will be the volume of local anesthetic received through PCEA per hour. Secondary outcomes will measure the total required local anesthetic required per hour, time to first PCEA bolus, labor pain scores, degree of motor blockade, mode of delivery, PCEA attempts and ratio of successful to unsuccessful attempts, frequency of hypotension, duration of first and second stages of labor and level of patient satisfaction.

Study design and recruitment:

The study will be a blinded randomized, controlled trial comparing the two regimens for labor analgesia that are currently used as standard of care at our institution: a patient will be assigned to receive either delivery of epidural medication ropivacaine 0.1% with fentanyl 2mcg/mL with PIEB + PCEA dosing method or CEI + PCEA dosing method. Potential participants will be recruited from the Duke University Birthing Center as they are admitted for labor with intention for vaginal delivery.

Inclusion criteria:

American Society of Anesthesiology (ASA) class 2 and 3 women
Nulliparous and Multiparous
Age > 18 yrs
gestational age > 36 weeks
singleton pregnancies
vertex pregnancies
In labor
cervical dilatation 2-7 cm at time of epidural placement
Pain score > 5

Exclusion criteria:

BMI > 50 kg/m²
history of past or current intravenous drug or chronic opioid abuse
chronic analgesic use
allergy or contraindication to any study medications
any maternal or fetal condition requiring planned assisted stage 2 delivery

Study Method:

After obtaining Duke University Institutional Review Board approval and informed consent, nulliparous or multiparous women in labor and cervical dilation between 2-7 cm desiring epidural for labor analgesia will be eligible to participate in this study. Subjects will be allocated to a study arm (CEI or PIEB) by computer-generated, random assignment placed in sealed opaque envelopes.

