The primary endpoint will be the total volume of local anesthetic received through PCEA per hour. Secondary outcomes will include need for physician interventions per hour, volume of clinician boluses required per hour, PCEA attempts per hour, PCEA boluses given per hour, unsuccessful PCEA attempts per hour, ratio of attempts/giver per hour and motor blockade measured by the lowest recorded modified Bromage scale, frequency of hypotensive events, mode of delivery, labor pain scores and patient satisfaction.

Statistical Analysis:

Data from a pilot study suggested that the mean (SD) PCEA volume used per hour was 6 (3) ml with CEI and 4 (3) ml with PIEB. A sample size of 44 patients per group will have an 80 % power at alpha=0.05 to identify this difference. To account for drop-outs and catheter failures, we will aim to enroll 200 subjects to have 60 completed patients per group. Randomization will be stratified according to parity (nullipara or multipara). Continuous data will be analyzed using kruskal wallis test or t test as appropriate. Categorical data will be analyzed using Chi-square test or Fisher's exact test as appropriate.

Subject identification, recruitment and compensation:

Patients presenting for spontaneous or induced delivery will be screened. Those eligible will be approached to participate in the study. A member of the healthcare team known to the subject will introduce the study. There will be no compensation to the subjects as a result of participation in this study.

Subject competency:

Only competent subjects will be approached to participate in this study.

Costs to Subject:

There will be no additional cost to the subjects as a result of participation in this research study.

Data Storage & Confidentiality:

Study records will remain confidential as required by law. Federal Privacy regulations ensure privacy, security and authorized access. Patient identifiers including but not limited to name, social security number, address, and telephone number will not be disclosed outside of the Duke University Health System (DUHS). For records shared with parties outside of DUHS, patients will receive a unique code number. The key to the code will be kept in a locked file in [name] office.

Data Integrity:

The data will be housed on the Department of Anesthesia's Parnassus server and the PI, and study team members will have access to the study data.

Data monitoring:

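### Randomisation is stratified by parity but no planned test uses parity; if parity predicts PCEA use, precision is lost that would cost almost nothing to keep

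*Combined protocol and SAP*

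**What the plan says.** The Statistical Analysis section of the combined protocol and SAP sets the stratification factor: "Randomization will be stratified according to parity (nullipara or multipara"). Two sentences then make up the whole analysis plan: "Continuous data will be analyzed using kruskal wallis test or t test as appropriate" and "Categorical data will be analyzed using Chi-square test or Fisher's exact test as appropriate". None of these tests uses the stratum, and choosing among them as appropriate does not bring parity in. No regression, covariate adjustment, stratified test or parity subgroup analysis appears elsewhere in the document.

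On balance, the Study Method section says "Subjects will be allocated to a study arm (CEI or PIEB) by computer-generated, random assignment placed in sealed opaque envelopes". Neither section mentions blocking within strata. The Statistical Analysis section also expects heavy attrition: "we will aim to enroll 200 subjects to have 60 completed patients per group".

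**The concern.** Stratifying by a factor is worthwhile mainly when the factor is expected to predict the outcome. If parity predicts hourly PCEA volume, an unadjusted test leaves the between-parity variation in its error term. How the loss appears depends on how evenly parity is split between arms in the analysed set:

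- **Tight balance.** The arm difference is in truth less variable than the unadjusted standard error says. The test is conservative and its confidence interval too wide.
- **Loose balance.** The test keeps its nominal error rate, but the estimate carries chance parity imbalance and is less precise than it could be.

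Because no blocking is described and 80 of 200 enrolled women are expected not to complete, either situation could arise. What is at stake is precision, not validity.

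**Working it through.** **Inputs from the Statistical Analysis section.** Primary endpoint: "The primary endpoint will be the total volume of local anesthetic received through PCEA per hour". Pilot data: "mean (SD) PCEA volume used per hour was 6 (3) ml with CEI and 4 (3) ml with PIEB", so a difference of 2 mL/h and SD 3. Planned completers: 60 per group, so attrition of 1 − 120/200 = 40%.

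**The plan's own figure.** It states: "A sample size of 44 patients per group will have an 80 % power at alpha=0.05 to identify this difference". The normal formula at two-sided 0.05 (sidedness is not stated) gives n = 2(1.960 + 0.842)² × 3²/2² = 35.3, so 36 per group; the t test needs 37. So 44 does not reproduce, but it errs on the safe side: t-test power is 87.1% at 44 per group and 95.2% at 60. This does not affect the parity point.

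**Assumptions not in the documents.** Half the women nulliparous, equal allocation, normal data, and a parity gap g of 1, 2 or 3 mL/h with the total SD held at 3. The share of variance due to parity is R² = (g²/4)/9, and the within-parity SD is √(9 − g²/4).

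**Precision and type I error under exact balance, 60 per group.**

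- Inflation of the unadjusted standard error = 1/√(1 − R²) − 1.
- Half-width = t × SD × √(2/60), with t about 1.98. Unadjusted: 1.98 × 3 × 0.1826 = 1.08.
- Two-sided type I error of the unadjusted test = 2[1 − Φ(1.96/√(1 − R²))].

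| Parity gap (mL/h) | R² | Within-parity SD | SE too large by | Half-width, unadjusted to adjusted | Type I error, unadjusted |
|---|---|---|---|---|---|
| 1 | 0.028 | 2.96 | 1.4% | 1.08 to 1.07 | 4.7% |
| 2 | 0.111 | 2.83 | 6% | 1.08 to 1.02 | 3.8% |
| 3 | 0.25 | 2.60 | 15% | 1.08 to 0.94 | 2.4% |

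Simulation of the exact-balance case gave type I errors of 4.6%, 3.8% and 2.4%.

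**Looser balance.** Two further cases were simulated: 100 per arm split evenly by parity with 40 per arm then lost at random, and no blocking, with parity drawn independently in each arm. There were 100,000 trials per scenario for exact balance and for no blocking, and 60,000 for the attrition case. Type I error of the unadjusted test for gaps of 1, 2 and 3 mL/h was 4.7%, 4.2% and 3.3% with attrition, and about 5% throughout without blocking. The model with arm and parity held 4.9 to 5.1% in all nine scenarios.

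**Power at 2 mL/h, 60 per group, unadjusted to adjusted.**

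| Parity gap (mL/h) | Exact balance | Balanced, then 40% lost | No blocking |
|---|---|---|---|
| 1 | 95.4 to 95.7% | 95.2 to 95.5% | 95.1 to 95.4% |
| 2 | 96.1 to 97.0% | 95.7 to 97.0% | 95.1 to 96.9% |
| 3 | 97.2 to 98.7% | 96.4 to 98.7% | 95.2 to 98.7% |

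The gain runs from 0.3 points (95.4 to 95.7) to 3.5 points (95.2 to 98.7).

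**Where it would matter more (exact balance).** With 44 completers per group, approximate power goes from 87.6 to 88.0%, 88.7 to 90.6% and 90.6 to 94.6%, gains of roughly 0.4, 2 and 4 points. With 60 per group and an illustrative true difference of 1.55 mL/h, which is not the planned effect, the gain is about 1 to 7 points.

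**Cost if parity is irrelevant.** Residual degrees of freedom fall from 118 to 117, which raises the critical t value by about 0.01%.

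**The case against.** The plan is valid as written. The unadjusted test errs, if at all, in the safe direction, and power is about 95% with 60 completers per group, so no conclusion is threatened at the planned effect. The benefit rests on an association the documents never report: the Background notes only that earlier studies enrolled mostly nulliparous women. The 3 mL/h gap, which drives the largest figures, is a full SD and 1.5 times the planned treatment difference. At 1 mL/h the gain is negligible. All of this stands, and it is why the point ranks low.

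A second objection concerns normality. PCEA comes in 8 mL boluses (Study Method), while the pilot means are 6 and 4 mL/h, or 6/8 = 0.75 and 4/8 = 0.5 of a bolus per hour on average. Hourly volume may therefore be skewed or contain zeros, and the rank route may be the one used. This also stands: the figures above describe the t-test route, and the gain from a stratified rank test has not been quantified. It limits the numbers but does not undo the case for analysing by the stratum.

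A third objection is that changing the categorical tests rests on convention, since no gain has been calculated for those outcomes. That is fair, and that part is optional.

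**Conclusion.** The concern holds, as a free improvement of low severity. Parity is used to randomise and then dropped from every planned test. There is no bias, no inflation of false positives, and no threat to the primary comparison at 2 mL/h.

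The clearest benefit is a narrower interval. Under exact balance its half-width falls by about 1%, 6% or 13% (1.0845 to 1.0695, 1.0226 or 0.9393 mL/h before rounding) for gaps of 1, 2 or 3 mL/h. The power gain is small because the base is already high; it would count for more with fewer completers or a smaller true effect. These sizes depend on the assumed parity gap, an even parity split and normal data. With no parity effect the gain is zero.

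**What to change.** State in the Statistical Analysis section that the primary analysis of PCEA volume per hour is a linear model with arm and parity stratum, reporting the adjusted difference with its 95% confidence interval. Settle this before outcome data are seen, so that neither the adjustment nor the choice between mean-based and rank-based analysis depends on the results. Wherever a rank test is kept, use the van Elteren test stratified by parity. For categorical outcomes, the matching choice is the Cochran-Mantel-Haenszel test stratified by parity; this is for consistency with the design, and no size of gain is claimed.

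The cost is SAP wording and one degree of freedom. Parity is already recorded for randomisation, so no new data and no change in trial conduct are needed.

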Epidural catheters will be placed at the L3/4 or L4/5 interspace with 4 cm of catheter being left in the epidural space. If the subject experiences an inadvertent dural puncture during epidural placement, she will be removed from the study. Epidural analgesia will be initiated and maintained with a solution of ropivacaine 0.1% with fentanyl 2 mcg/ml. After the initial epidural loading dose of 20 mL is administered in incremental fashion, patients will receive either 6 mL every 45 minutes in the PIEB arm (first bolus 30 minutes after epidural initiation) or 8mL/hr of continuous infusion beginning immediately after the loading dose for the maintenance of analgesia in the CEI arm, both of which are standard of care at our institution. All study participants will be provided with PCEA set to 8mL boluses with a 10-minute lockout period. The maximum amount of PCEA analgesia will be set to a 1-hour maximum of 45mL. A script will be provided to anesthesia providers so that the same explanation about the use of the PCEA is provided to all subjects. Monitoring of patients will be with blood pressure measurements every 2 minutes for 15 minutes and then every 15 minutes afterwards, and with continuous heart rate and pulse oximetry as per standard of care. If the parturient does not achieve adequate

analgesia with a pain score ≤ 2 at 30 minutes, the catheter will be considered unsatisfactory, and the subject will be withdrawn from the study. Pain scores and Bromage scores will be collected at 30 minutes after epidural initiation and then every 2 hours until delivery. If the patient has inadequate analgesia, despite activating the PCEA twice in the last 20 minutes, physician boluses will be administered using 5 ml of ropivacaine 0.2% every 10 minutes. If the patient does not have adequate analgesia after 10 ml ropivacaine 0.2%, the catheter will be considered unsatisfactory if there is no bilateral sensory level at this stage and the patient will be removed from the study. If there is bilateral sensory level to at least T10 after the ropivacaine boluses, and the patient complains of pressure, fentanyl 100 mcg will be given epidurally. If the patient does not achieve a pain score ≤ 2 after fentanyl, the patient will be removed from the study. The study will begin with epidural insertion and terminate with delivery. Per standard of care, each participant will be evaluated 24-hours post-partum to assess for any adverse effects.

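### Time to first PCEA bolus is censored at delivery for women who never use PCEA, but the plan has no rule for them and names only a t or Kruskal-Wallis test

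*Combined protocol and SAP*

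**What the plan says.** All places are in the combined protocol and SAP.

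- **Purpose of the study** includes this outcome among the secondary ones: "time to first PCEA bolus, labor pain scores, degree of motor blockade, mode of delivery".
- **Study Method** makes PCEA available on demand to everyone: "All study participants will be provided with PCEA set to 8mL boluses with a 10-minute lockout period". It fixes the end of observation: "The study will begin with epidural insertion and terminate with delivery". For a woman whose pain score is above 2 at 30 minutes it says "the catheter will be considered unsatisfactory, and the subject will be withdrawn from the study".
- The **last paragraph of Study Method** gives a second list, which opens "Secondary outcomes will include need for physician interventions per hour, volume of clinician boluses required per hour". Time to first PCEA bolus is not in it.
- **Statistical Analysis** gives one rule for continuous outcomes: "Continuous data will be analyzed using kruskal wallis test or t test as appropriate". Categorical data get a chi-square or Fisher's exact test. No time-to-event method is named, and no value or rule is given for a woman with no PCEA bolus.
- The same section gives the pilot figures, "PCEA volume used per hour was 6 (3) ml with CEI and 4 (3) ml with PIEB", and the target, "we will aim to enroll 200 subjects to have 60 completed patients per group".

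**The concern.** A woman who delivers without using PCEA is right-censored: her time to first use is known only to exceed her time to delivery. A t or Kruskal-Wallis test needs a number or a rank for her, so someone must choose to drop her, enter her delivery time, or rank her last. The plan does not make that choice, and it also leaves open which test is used.

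The choice matters in two ways.

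- **Dropping** removes the women with the best result. If PIEB lowers PCEA use, more of them come from the PIEB arm, and the arms look more alike than they are.
- **Choosing after seeing the data** gives several chances at a small p-value.

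A woman withdrawn at 30 minutes before any PCEA use raises the same question if she is in the analysis set. The target is worded in terms of completed patients, so it is unclear whether she would be.

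**Working it through.** **The plan's own figure.** There is none for this outcome. The stated 44 per group is for the primary outcome and does not bear on this point.

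**Inputs from the documents.** Pilot PCEA use 6 mL/h (CEI) and 4 mL/h (PIEB); trial bolus 8 mL; 60 completed women per arm; alpha 0.05 (two-sided assumed).

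**Assumptions.** Labour length after the epidural and the share of never-users are not given. Follow-up of 4, 6 and 10 h is used as a range. The pilot's bolus size is not stated either. Dividing by 8 mL gives 0.75 vs 0.50 boluses/h. The group's retrospective study (Background) used 5 mL, which would give 6/5 = 1.2 and 4/5 = 0.8 boluses/h. Both are shown.

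**Step 1: effect of dropping on the mean.** With a constant rate r and fixed follow-up h:

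- the never-user share is exp(-r h);
- the mean time among users is 1/r - h exp(-r h)/(1 - exp(-r h)).

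At 8 mL the true means are 1/0.75 = 1.333 h and 1/0.50 = 2.000 h, a difference of 0.67 h. Among users only:

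| Follow-up | CEI | PIEB | Difference |
|---|---|---|---|
| 4 h | 1.124 | 1.374 | 0.25 h |
| 6 h | 1.266 | 1.686 | 0.42 h |
| 10 h | 1.328 | 1.932 | 0.60 h |

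If nobody uses PCEA in the first 30 minutes, the differences are 0.20, 0.38 and 0.59 h. At 5 mL the true difference is 1/0.8 - 1/1.2 = 0.42 h, and the same formula gives 1.080 - 0.800 = 0.28 h at 4 h.

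**Step 2: expected never-users.** With follow-up varying between women (gamma, shape 4, mean h), the count per arm is 60(1 + r h/4)^-4. CEI vs PIEB at 4, 6 and 10 h:

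- 8 mL: 6.4 vs 11.9, 2.9 vs 6.4, 0.9 vs 2.3
- 5 mL: 2.6 vs 5.7, 1.0 vs 2.6, 0.2 vs 0.7

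**Step 3: power.** Simulation with 60 per arm, exponential times, the same gamma follow-up (minimum 0.5 h) and unstratified tests. Monte Carlo error is about 1.3 points with 6000 trials; a range in a cell comes from repeated runs. KW is Kruskal-Wallis. Entries are for mean follow-up 4/6/10 h.

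| Setting | KW, dropped | KW, ranked last | Log-rank |
|---|---|---|---|
| 8 mL bolus | 21-23/32/41% | 42-44/46/48% | 51-53/57/57-60% |
| 5 mL bolus | 33/39/45% | 47/47/48% | 56/58/60% |
| 8 mL, rates vary between women (gamma variance 0.5) | 15/18/23% | 31-33% | 31-33% |

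For the t test at 8 mL, power is 26/38/50% with never-users dropped and 48/53/58% with delivery time entered. Exponential times give proportional hazards and so favour log-rank; the last row relaxes this.

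**Step 4: type I error** (both arms 0.6 boluses/h).

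- One prespecified handling, equal follow-up: about 5% for each.
- Smallest p among three KW handlings: about 6-9%. If the t test is open too (five handlings): about 9-12%.
- Dropping, with PIEB follow-up 25% shorter (assumed): about 9-12% at 4 h, falling to about 5-6% at 10 h.
- Dropping, with follow-up 22 minutes shorter (the second-stage reduction reported in Background): about 6%.

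**Step 5: does the direction always hold?** No. With lognormal labour of median 6 h and 8 mL boluses, dropping turns the true mean ratio of 1.50 into 1.35. If PIEB labour were 2 h longer, the ratio among users is 1.49, so almost nothing is lost. If a further 25% of CEI and 10% of PIEB women never needed PCEA, KW with never-users dropped rejects in 29% of trials against 10% for log-rank, so dropping would overstate the contrast.

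**The case against.** The strongest reply is that Kruskal-Wallis is not a wrong test here. With never-users ranked last it is valid when follow-up is similar. It equals log-rank when women differ in PCEA rate, which the pilot SD of 3 on means of 4 and 6 makes plausible. The words allowing the appropriate test leave room for it. This stands: the defect is the missing rule for never-users, and log-rank is the better default, not the only acceptable method.

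A reader might infer three stronger things that the documents do not support.

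- *The trial will drop never-users and so bias the result against PIEB.* No section says they will be dropped, and the direction depends on labour length and on which arm has more never-users.
- *False positives will run at 9-12%.* That is the upper end, reached only by choosing among both tests and all handlings afterwards, or by dropping in short labours with clearly unequal follow-up.
- *The loss is large whatever the inputs.* It rests on an assumed labour length and on pairing pilot volumes with this trial's bolus. With 5 mL boluses and 10 h follow-up, dropping costs Kruskal-Wallis about 3 points (48% to 45%).

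It is also fair that the endpoint has limited power under any of these methods in the main settings: at most about 60%.

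**Conclusion.** The point holds as a gap in the rule for one secondary outcome. The outcome is censored at delivery, and the only applicable rule does not say what to do with women who never use PCEA. If they were dropped, with PCEA use as in the pilot and similar labour length, Kruskal-Wallis power would fall by roughly 20 points against ranking them last at a 4 h mean (8 mL bolus), and by about 3 to 7 points at 10 h. These sizes are illustrations; labour length, bolus rate and the distribution of times are assumed. Type I error is protected by any single handling fixed in advance, provided follow-up is similar between arms. The primary outcome and the sample size are untouched. Severity is minor: this is a cheap improvement.

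**What to change.** For this outcome, replace the t/Kruskal-Wallis rule with the following.

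- Measure time from epidural initiation and keep every analysed woman, censored at delivery if she has not used PCEA.
- Analyse by Kaplan-Meier with a log-rank test stratified by parity, as randomised. A simpler acceptable alternative is Kruskal-Wallis with never-users ranked last. Name one of the two in advance.
- State that censoring at delivery targets the rate of first use while still in labour.
- Report the number of never-users per arm.
- State how women removed for inadequate analgesia before first use are handled. Censoring them may be informative, because removal depends on pain, so add a sensitivity analysis.
- Reconcile the secondary outcome lists in Purpose of the study and Study Method.

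The cost is a few lines of wording and slightly more analysis. Log-rank gives no difference in hours, so Kaplan-Meier medians should be reported with it. No new data are needed, provided the times of epidural initiation, first PCEA use, delivery and removal are recorded.

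### Randomisation is stratified by parity, but the primary comparison ignores parity and every other pre-treatment variable: valid, but less precise than it could be

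*Combined protocol and SAP*

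**What the plan says.** The Statistical Analysis section names the primary endpoint just before the heading ("The primary endpoint will be the total volume of local anesthetic received through PCEA per hour") and covers all continuous outcomes in one sentence: "Continuous data will be analyzed using kruskal wallis test or t test as appropriate". No covariate is named. The sentence immediately before it stratifies randomisation by parity, nulliparous or multiparous, but parity does not reappear in the analysis.

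The population is mixed in other ways too. The inclusion criteria admit women with "cervical dilatation 2-7 cm at time of epidural placement" and a pain score above 5. The recruitment section states: "Patients presenting for spontaneous or induced delivery will be screened". These three characteristics appear only as eligibility or screening items. No list of baseline data is given, and the first scheduled pain score in Study Method is 30 minutes after epidural initiation.

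The sample size rests on a pilot in which the "mean (SD) PCEA volume used per hour was 6 (3) ml with CEI and 4 (3) ml with PIEB".

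**The concern.** Stratifying by a factor and then analysing as if it did not exist wastes part of what the stratification achieved. If parity predicts PCEA use and the arms are balanced on it, the difference between arms varies less from trial to trial than the unadjusted standard error claims. The test then rejects too rarely under the null and the confidence interval is too wide. The sponsor presumably considered parity prognostic, or it would not have stratified by it.

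The same reasoning extends, less securely, to dilatation, pre-epidural pain and labour type. Each could plausibly predict PCEA demand, or the time to delivery that forms the denominator of mL/h. What is at stake is precision, not validity.

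**Working it through.** **Inputs from the plan.** Difference 6 − 4 = 2 mL/h and common SD 3; alpha 0.05, taken as two-sided because the plan does not say; "44 patients per group" for the calculation, and 60 completers per group as the target ("we will aim to enroll 200 subjects to have 60 completed patients per group").

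**Assumed inputs.** R², the share of variance explained by the covariates. The documents give none, so 0 to 20% is shown. For parity, I also assume that stratification balances the arms and that withdrawals leave the completers balanced. The plan describes computer-generated allocation in envelopes but no blocking, so this is not certain.

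**1. The plan's own figure.** The plan states: "A sample size of 44 patients per group will have an 80 % power at alpha=0.05 to identify this difference". The usual formula gives n = 2 × (1.96 + 0.8416)² × 3² / 2² = 35.3, so 36 per group, or 37 with the noncentral t. The stated 44 gives 87.1% power and 60 gives 95.2%. So 44 does not follow from the stated inputs unless an unstated allowance was added. The discrepancy is conservative and does not affect this point.

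**2. Effect of ignoring the parity stratum (60 per group).** The unadjusted standard error is 3 × √(2/60) = 0.548 mL/h. With parity balanced, the true standard error is 0.548 × √(1 − R²). The true alpha is 2 × [1 − Φ(1.96/√(1 − R²))].

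| Parity R² (assumed) | True SE | 1.96/√(1 − R²) | True alpha | 95% CI half-width if adjusted |
|---|---|---|---|---|
| 0 | 0.548 | 1.960 | 0.050 | 1.07 |
| 5% | 0.534 | 2.011 | 0.044 | 1.05 |
| 10% | 0.520 | 2.066 | 0.039 | 1.02 |
| 20% | 0.490 | 2.191 | 0.028 | 0.96 |

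The half-width is 1.96 × true SE, in mL/h. If R² is zero, adjusting for parity costs one degree of freedom and power stays at 95.2%.

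**3. Adding three unstratified covariates.** Randomisation does not force balance on dilatation, pain score and labour type, so their chance correlation with arm inflates the variance. With N = 120 and k = 3, the factor is approximately (N − 4)/(N − 4 − k) = 116/113 = 1.027. Power comes from the noncentral t with residual SD 3 × √(1 − R²), this factor, and 120 − 6 = 114 degrees of freedom.

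| R², all four covariates (assumed) | Unadjusted power | Adjusted power |
|---|---|---|
| 0 | 95.2% | 94.7% |
| 5% | 95.2% | 95.6% |
| 20% | 95.2% | 97.9% |

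The break-even R² is therefore a little above 2%: at 2% the same calculation gives 95.1%.

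**4. Size of chance imbalance.** For a factor present in half the women, the SD of the between-arm difference in proportions at 60 per arm is √(0.25 × 2/60) = 0.091. The chance of a gap above 10 percentage points is about 27%. Such gaps are ordinary, and the unadjusted standard error already includes them.

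**The case against.** The strongest reply is that nothing is broken. A two-group test in a randomised trial is valid, power is already about 95% at the planned 60 completers, and no figure in the documents shows that any covariate predicts PCEA use. Eligibility also truncates dilatation and pain score, which limits what they can explain. Most of this stands: the point concerns efficiency and its size is unknown. It does not dispose of parity, which must be known at randomisation and can be adjusted for at almost no cost even if it proves uninformative. The 95% also depends on the pilot difference. At an assumed 1.5 mL/h, power at 60 per group is 77.5%, and would be 79.6-85.9% with R² of 5-20% from parity alone.

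A reader might infer two stronger things.

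- **That labour type, dilatation and pain score are already recorded at baseline, so using them is free.** The documents do not say so. They are ascertained for eligibility or screening, but no baseline data item is listed. Adjusting for them also carries the small cost in step 3.
- **That chance imbalance in an unstratified factor biases the result.** It does not. Over repeated randomisation the unadjusted estimate is unbiased, and type I error is not inflated.

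**Conclusion.** The point holds as an efficiency recommendation. The planned primary test omits the trial's own stratification factor and all other pre-treatment variables. It remains valid, but is conservative if parity is prognostic and balanced: true alpha is about 0.044 to 0.028 for an assumed parity R² of 5-20%. If stratification does not in fact balance the completers, alpha moves back towards 0.05, and adjustment still recovers the variance that parity explains.

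For the full covariate set at 60 per group and 2 mL/h, power goes from 95.2% to about 95.6-97.9% at R² of 5-20%, and falls to about 94.7% at R² of zero. The documents support adjusting for parity. They support the other three covariates only on condition that the values are captured. They do not support calling the planned analysis invalid or the trial underpowered on this account.

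**What to change.** In the Statistical Analysis section, before unblinding:

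1. Pre-specify the primary analysis as a linear model of PCEA mL/h on arm and parity stratum, with robust standard errors.
2. Report the adjusted mean difference with its 95% CI.
3. Keep the unadjusted t or rank test as a sensitivity analysis. This also removes the open choice between the two tests for the primary result.
4. Ask the sponsor to confirm whether dilatation at placement, pre-epidural pain score and spontaneous versus induced labour are captured before randomisation. If so, name them as covariates in advance; if not, leave them out.

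The parity change takes one or two sentences and needs no new data or extra patients. The other covariates may need a few case-report-form fields, and cost about half a point of power if they prove uninformative.
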